## **8.9. Provisions for Remote Assessment Methods**

For emergency situations where there are extenuating circumstances that prohibit physically coming to the clinical site or when the safety of subjects may be compromised by physical visits to the site, remote assessments may be considered after discussion with the Sponsor.

## **9. STATISTICAL CONSIDERATIONS**

### **9.1. Sample Size Determination**

A total of 48 subjects will be randomized 1:1:1:1 to receive 1 of the 3 dosing regimens of MNK6106 or the comparator rifaximin for 5 days. This study is exploratory in nature. Prematurely discontinued subjects will not be replaced.

### **9.2. Populations for Analysis**

For the purposes of analysis, the following populations are defined

- The Modified Intent-to-Treat (mITT) Population will include all randomized subjects who receive at least 1 study treatment and who contribute any postbaseline PD data to the study.
- The Safety Population will include all subjects who receive 1 or more study treatments.
- The PK population will consist of all subjects in the Safety Population with at least 1 evaluable plasma concentration following treatment with MNK6106.

### **9.3. Statistical Hypothesis and Analyses**

This is an exploratory study and so there is no statistical hypothesis to test.

#### **9.3.1. Pharmacodynamic Analyses**

The descriptive statistics for PD variables, which are the plasma AMM level and the change of the plasma AMM level from baseline, will be used by treatment and by visit. The Mallinckrodt treatments will also be combined for display. The summaries will be based on the mITT population.

For continuous variables, descriptive statistics will include the following: the number of subjects reflected in the calculation (n), mean, median, standard deviation, minimum, and maximum. The 95% confidence intervals will be presented.

The graphic for PD variables by treatment and by visit will also be provided.

---

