### 3. OBJECTIVES AND ENDPOINTS

#### 3.1. Primary Objective/Endpoint

Primary Objective	Endpoint
To evaluate the pharmacological activities through plasma AMM concentration as a PD marker following oral administration of MNK6106 with rifaximin as a comparator in subjects with hepatic cirrhosis and a history of prior episodes of HE.	Absolute and percentage change of plasma AMM from baseline.

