### 3.3. Outcome Measures

Outcome measures are identified to facilitate clinical trial registration and patient access to basic results disclosed on public clinical trial registries.

The primary outcome measure in the study is the number of participants with a change in ammonia at Day 5.

The secondary outcome measure in the study is the number of participants with adverse events or deaths during the study.

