**8. STUDY ASSESSMENTS AND PROCEDURES****8.1. Screening (Day -28 to Day -1)**

Subjects should be screened within 28 days prior to administration of the first dose of study treatment on Day 1. Written consent must be obtained from each subject before the initiation of any screening procedure. A sufficient number of subjects will be screened to identify 48 subjects fulfilling all entry criteria.

Once written consent has been obtained, the following procedures will be performed at the Screening evaluation:

- Review inclusion/exclusion criteria.
  - Record demographics.
  - Record medical/surgical history (including history of exposure to COVID-19).
  - Record all prior medication/therapies.
  - Record concomitant medications/therapies
  - Perform a complete physical examination.
  - Measure the subject’s height, weight and waist circumference.
-

- 
- Measure the subject's vital signs.
  - Record an electrocardiogram (ECG).
  - Collect a blood sample for plasma AMM. Results will be used to determine eligibility for Inclusion Criterion #5.
  - Collect samples for chemistry, hematology, and urinalysis.
  - Perform a urinary drug screen including a screen for methadone at screening only.
  - Collect blood samples for hepatitis and HIV serology.
  - Record the Conn, MELD, HESA and C-P scores.
  - Record/collect AEs/SAEs (including AEs of special interest [AESI]) after the consent process is completed.
  - Perform a serum pregnancy test/follicle stimulating hormone (FSH) test (FSH is required for postmenopausal women).

A postmenopausal state is defined as no menses for 12 months without an alternative medical cause. A high FSH level in the postmenopausal range (greater than 40 mIU/mL) may be used to confirm a postmenopausal state in women not using hormonal contraception or hormonal replacement therapy (HRT). However, in the absence of 12 months of amenorrhea, a single FSH measurement is insufficient. Females on HRT and whose menopausal status is in doubt will be required to use one of the non-estrogen hormonal highly effective contraception methods if they wish to continue their HRT during the study. Otherwise, they must discontinue HRT to allow confirmation of postmenopausal status before study enrollment.

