### 8.3. Treatment Period (Week 1; Day 1 to Day 5/ET) and Day 6 (Discharge)

After randomization, subjects will enter the study, and receive active treatment (1 of 3 MNK6106 dose regimens or rifaximin) for 5 days. Subjects will be confined to the study center overnight during the treatment period and discharged on Day 6. The following procedures will be carried out on Days 1, 2, 3, 4 and 5 unless otherwise stated:

- Perform a limited physical examination (Day 1 only).
- Record the subject's weight and waist circumference (Day 1 and Day 6 only).
- Record the subject's vital signs (Day 1 through Day 6).
- Record ECG (Days 1, 3 and 5/ET only) at 1 hour after the last dose ( $\pm$  15 minutes). Complete the ECG prior to the PK sample collection if the timing is the same.
- Collect blood samples for plasma AMM (to be drawn on Days 1, 3 and 5/ET only, predose in the morning immediately before breakfast and 4 hours ( $\pm$  15 minutes) after the morning dose), as well as on the day of the final visit.
- Collect a blood sample for plasma PAA, ORN and PAGN (to be drawn on Days 1, 3 and 5/ET only). A baseline sample will be drawn prior to the first dose on Day 1 (within 15 minutes prior to the morning dose) and then prior to (with 10 minutes) and 1 hour ( $\pm$  15 minutes) after the last dose on Days 1, 3, and 5/ET.
- Collect a urine sample for PAGN. For each 24-hour collection following the first dose of the day, all urine will be collected during the specified intervals, with the last collection for Day 5/ET being collected on Day 6. A baseline urine sample will also be collected predose on Day 1.
- Collect samples for chemistry, hematology, (Days 1 through 6) and urinalysis (Days 1 through 5 only).
- Record the Conn, MELD, HESA and C-P scores (Days 1 through 6).
- Perform study drug dosing.
- Record all concomitant medications/therapies (Days 1 through 6).
- Record and assess AEs/SAEs, including AESI (Days 1 through 6).

On the Day 6 visit (discharge):

If no clinical or laboratory abnormalities are observed, subjects will be discharged from the study on the morning of Day 6. The 24-hour urine collection for PAGN will be completed on Day 6 at the end of confinement.

Additional follow-up visits will be scheduled if a subject shows any clinical or laboratory abnormalities at this visit, as deemed appropriate by the investigator/designee (classified as unscheduled visits).

---

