#### **8.5. Pharmacodynamic and Pharmacokinetic Assessments**

##### **8.5.1. Pharmacodynamic Sampling**

Plasma AMM data are extremely important, but these samples are exquisitely sensitive. For this reason, great care must be taken with the collection, handling, processing, and storage of plasma AMM samples.

Samples for plasma AMM levels will be drawn at screening, on Days 1, 3 and 5/ET predose in the morning immediately before breakfast and 4 hours ( $\pm$  15 minutes) after the morning dose, and at the final visit.

Before the blood draw to collect a sample for venous AMM, place the collection tube on ice for at least 10 minutes. Immediately after drawing blood, *gently* invert the specimen approximately 8 to 10 times, place the specimen on wet ice, separate the plasma by refrigerated centrifugation as soon as possible, and freeze the plasma specimen for analysis at  $-70^{\circ}\text{C}$  or colder immediately after centrifugation. This specimen will be processed by the laboratory or by trained personnel

---

per facility standard operating procedures. All plasma for AMM testing must be prepared and stored in a -70°C or colder freezer with the greatest speed feasible. All frozen samples will be transported to a laboratory testing site. Review the Laboratory Manual/sample handling guide for complete information.

Venous AMM draws are predicated on timing, which is of paramount importance; however, for subjects able to eat, it is preferable to obtain the blood sample prior to food intake (if feasible). *Because of the exquisite delicacy of this analyte stringent before drawing, blood draw and specimen processing parameters must be adhered to; documentation of each step of preanalytic specimen preparation and processing is required for each time point inclusive of date and time for each step recorded on the laboratory requisition and source documentation.* It is essential that venous AMM plasma samples be correctly prepared to avoid spurious results; if the specimen integrity is compromised by inappropriate handling, it would be preferable not to send that sample to the laboratory for analysis.

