### 8.5.3. Urine Sampling for PAGN Measurement

Urine collection (with start/end time and volume recorded) for measurement of PAGN, the study drug metabolite excreted in urine, will be collected for 24 hour intervals following the first dose of the day. Collect a baseline sample prior to initial dosing on Day 1.

- Urine collection will start at the initiation of study drug (predose urine sample).
- The next collection interval time starts immediately following the first dose administration of the day. For example, if the first dose of the day is administered at 8 AM, all urine volume will be collected through the following morning at approximately 8 AM.
- Measure total volume during each time interval, document collection start/stop times, obtain 2 aliquots and freeze immediately as per Laboratory Manual instructions.
- The final urine collection time interval on Day 5/ET is from the first dose on Day 5/ET until the following day, Day 6 (24 hour interval).

Urine samples for analysis of PAGN elimination will be collected into pre-labeled polyethylene containers for each collection interval. For each 24-hour collection, all urine will be collected during the specified intervals in the Schedule of Study Events (Table 1). Subjects will be asked to void at the end of each collection interval, but if a subject voids more than once in a single collection interval, each void will be added to the collection container for that interval and thoroughly mixed. The start and stop time of each collection will be recorded on the eCRF. Care should be taken to avoid spillage of urine outside of the collection vessel.

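### Section 9.3.1 plans no MNK6106-versus-rifaximin estimate or interval for ammonia, no baseline adjustment and no percentage change, although the primary objective names rifaximin as comparator

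*Combined protocol and SAP*

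**What the plan says.** The primary objective (Sections 1.1 and 3.1) is to evaluate pharmacological activity through plasma ammonia after "oral administration of MNK6106 with rifaximin as a comparator". The endpoint is "Absolute and percentage change of plasma AMM from baseline". Section 3.1 names no visit. Section 3.3 does: "The primary outcome measure in the study is the number of participants with a change in ammonia at Day 5".

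For ammonia, Section 9.3.1 plans "The descriptive statistics for PD variables, which are the plasma AMM level and the change of the plasma AMM level from baseline", by treatment and by visit in the mITT population. The statistics are n, mean, median, SD, minimum, maximum and 95% confidence intervals. The three MNK6106 arms are also pooled for display. No difference between arms, model or covariate is named, and percentage change is not listed.

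Ammonia is sampled at screening, on Days 1, 3 and 5/ET "predose in the morning immediately before breakfast and 4 hours" after the morning dose, and at the final visit (Section 8.5.1). No section says which sample is the ammonia baseline. For the screening sample, Section 8.1 says "Results will be used to determine eligibility for Inclusion Criterion #5". For plasma PK, Section 8.3 says "A baseline sample will be drawn prior to the first dose on Day 1", and for urine Section 8.5.3 says "Collect a baseline sample prior to initial dosing on Day 1".

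Sections 9.1 and 9.3 describe the study as exploratory with no hypothesis. Section 9.5 plans ANCOVA with multiple imputation for the Child-Pugh, MELD, Conn and HESA scores. Section 9.5.4 rules out imputation of PD data.

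**The concern.** A quarter of the subjects are randomized to rifaximin so that MNK6106 can be set against it, yet the plan states no estimate of that comparison. Three things follow.

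- **Side-by-side intervals are not an interval for the difference.** A reader who judges by whether two arm-level intervals overlap applies a cruder rule than the data allow.
- **An unadjusted contrast carries part of any chance baseline imbalance.** At 12 per arm the imbalance can be sizeable. Day 1 predose ammonia is already collected and could be used to adjust.
- **Choices stay open until the data are seen.** These are the contrast, the baseline, the Day 5 sample (predose or 4-hour) and the scale. The percentage-change half of the endpoint has no planned summary, and mean percentage change cannot be recovered from means and SDs of level and absolute change.

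**Working it through.** **Plan figures.** 48/4 = 12 per arm, and pooled MNK6106 is 3 × 12 = 36 against 12 (Section 9.1). No SD, effect size, power or precision target is given, so 48 itself cannot be reproduced. Section 2.2 says only that percentage change in ammonia was highly variable in an earlier study.

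**Separate intervals versus a difference** (in SDs of change):
- One arm's mean: t(0.975, 11)/√12 = 0.64.
- One regimen minus rifaximin: t(0.975, 22) × √(2/12) = 0.85.
- Pooled MNK6106 minus rifaximin: t(0.975, 46) × √(1/36 + 1/12) = 0.67.

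With equal SDs, two arm-level intervals stop overlapping only when the means differ by about 2 × 0.635 = 1.27 SD. The interval for the difference excludes zero from 0.85 SD.

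**Gain from baseline adjustment.** Assumptions, none from the documents: lognormal ammonia, log SD 0.4 or 0.5, baseline-to-Day-5 correlation ρ of 0.3 to 0.9, and an error variance pooled over four arms.

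In large samples, Var(ANCOVA)/Var(change) = (1 − ρ²)/(2(1 − ρ)) = (1 + ρ)/2. This is 0.65, 0.75, 0.85 and 0.95, with width ratios (square roots) of 0.81, 0.87, 0.92 and 0.97.

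At 12 per arm, 10,000 simulated trials per setting with no treatment effect (44 error df for change, 43 for ANCOVA) gave these mean 95% half-widths on the log scale, one regimen versus rifaximin:

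| ρ | Change, log SD 0.4 | ANCOVA, log SD 0.4 | Change, log SD 0.5 | ANCOVA, log SD 0.5 | Width ratio | ANCOVA wider in |
|---|---|---|---|---|---|---|
| 0.3 | 0.388 | 0.316 | 0.484 | 0.396 | 0.81–0.82 | 0.5% of trials |
| 0.5 | 0.327 | 0.287 | 0.409 | 0.358 | 0.88 | 2–3% |
| 0.7 | 0.254 | 0.237 | 0.317 | 0.296 | 0.93 | 11–12% |
| 0.9 | 0.146 | 0.144 | 0.183 | 0.181 | 0.99 | 44% |

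At log SD 0.4 and ρ = 0.5 the interval for the ratio is therefore the estimate multiplied and divided by exp(0.327) = 1.39 unadjusted, or by exp(0.287) = 1.33 adjusted. With 10 per arm the ratios are almost the same (0.82, 0.88, 0.94, 0.99).

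**Chance imbalance.** The SD of the difference in mean log baseline between two arms is SD × √(2/12), which is 0.163 or 0.204. The 95% range of the baseline geometric-mean ratio, exp(±1.96 × that SD), is 0.73 to 1.38 or 0.67 to 1.49. An imbalance of one such SD shifts the unadjusted change contrast by exp((1 − ρ) × SD) − 1. For ρ of 0.3, 0.5, 0.7 and 0.9 this is 12, 9, 5 and 2% (log SD 0.4) or 15, 11, 6 and 2% (log SD 0.5).

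**Why the log scale.** If the drug lowers ammonia proportionally, the untransformed spread differs by arm and a pooled error misstates the precision. Take assumed reductions across the three regimens and none on rifaximin. The nominal 95% interval for pooled MNK6106 versus rifaximin from an untransformed pooled-variance ANCOVA then covers about 92–94% (reductions of 10/20/30%) or 86–89% (30/40/50%). The log-scale model stays near 95% in both cases.

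**The case against.** The strongest reply is that the study is exploratory, with no hypothesis and no promise of an estimated difference. Arm-level summaries and a pooled MNK6106 display can serve a Phase 2a look at activity. This stands as a limit on severity. It answers a complaint about a missing test or missing power, which is not made here. It does not make an estimate with an interval less useful when the objective names a comparator.

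Other replies stand in part:

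- **The difference can be derived.** True for the unadjusted absolute change, which randomization leaves unbiased. It is not true for percentage change or for an adjusted contrast.
- **It may be in another document.** Section 9.5.2 refers to a statistical analysis plan that was not available. If the contrast is there, a cross-reference is enough.
- **Baseline is effectively known.** A reader might infer that screening and Day 1 predose are equally plausible baselines. The documents do not support that: screening ammonia serves eligibility, and the PK and urine baselines are Day 1 predose. One confirming sentence settles it. Regression to the mean from the entry threshold would act alike on randomized arms, so it does not bias the contrast.
- **The gain rests on assumptions.** It does, and it nearly disappears at ρ = 0.9.
- **ANCOVA in Section 9.5 proves little.** The amendment log shows those score analyses were added when the scores were secondary endpoints, a status later removed. The section shows only that exploratory status does not rule out a model in this plan.

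**Conclusion.** The point holds as a recommended improvement. Section 9.3.1 specifies no MNK6106-versus-rifaximin estimate or interval and no baseline adjustment, and it omits percentage change.

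Under the assumptions above, log-scale ANCOVA narrows the mean interval by about 18, 12, 7 and 1% at ρ of 0.3, 0.5, 0.7 and 0.9. The true correlation and SD are unknown, so the gain may be small. The gain in prespecification does not depend on them.

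A reader might infer that the primary comparison cannot be made or that the planned analysis is invalid. The documents do not support this: the design is declared exploratory, and the planned n, mean and SD give an unbiased unadjusted difference in absolute change. Confidence is medium, mainly because the separate statistical analysis plan was not seen.

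**What to change.** Add to Section 9.3.1:

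> Baseline plasma AMM is the Day 1 predose value. As an exploratory estimate without hypothesis testing, log AMM at Day 5 will be analysed by ANCOVA with treatment (4 levels) and log baseline AMM. This gives the ratio of geometric-mean Day 5/baseline AMM for each MNK6106 regimen, and for the pooled MNK6106 arms, versus rifaximin with 95% CI. One of the two Day 5 samples (predose or 4-hour) will be named as principal before data are seen; the other is supportive. Samples taken at premature discontinuation before Day 5 are not counted as Day 5 values. Subjects without a Day 5 value are not imputed (Section 9.5.4), and their number is given per arm.

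Keep the descriptive tables and add percentage change. The geometric-mean ratio is a different summary from mean percentage change and does not replace it. The discontinuation sentence is needed because Section 8.3 asks for the evaluations at premature discontinuation and Day 5 is labelled Day 5/ET.

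Naming one scale and one sample leaves 4 principal intervals. Reporting four contrasts on two scales at both times would give 4 × 2 × 2 = 16 with none leading. If a baseline-adjusted absolute difference is also wanted, use heteroscedasticity-robust or arm-specific variances, not a pooled error. If the separate statistical analysis plan already covers this, refer to it in Section 9.3.1.

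The cost is a few sentences and a few lines of code. All samples are already scheduled, so no subject, visit or blood draw is added.

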### 9.3.2. Pharmacokinetic and Pharmacodynamic Analyses

The descriptive statistics for concentrations of PAA, ORN and PAGN will be used by treatment and by PK sampling time. Urinary recovery of PAGN will be summarized by treatment and study day. Descriptive statistics will include the following: the number of subjects reflected in the calculation (n), mean, median, standard deviation, minimum, and maximum. The 95% confidence interval will be presented.

Population PK modeling will be developed with the PK data obtained from the study such as concentration of PAA, ORN and PAGN. Sources of variability contributing to the PK will be identified. Exposure response relationships describing the safety and AMM levels following treatment with MNK6106 will be explored.

### 9.3.3. Analysis Methods for C-P, MELD, Conn and HESA Scores

Details of C-P, MELD, Conn and HESA scores are provided in Section 9.5.

## 9.4. Liver Function Classification

Liver function classification details are provided in Section 10.6.

## 9.5. Other Analyses

Summary statistical analyses will be provided for demographics, medical history, physical examination, social history, and risk factor variables at baseline.

For C-P, MELD, Conn, and HESA scores:

- The change and percent change of C-P, MELD, Conn, and HESA scores by visit will be summarized and analyzed using multiple imputation with an analysis of covariance model, respectively.
- The percent of subjects with C-P (A, B, C), MELD (40+, 30-39, 20-29, 10-19, <9), Conn (0,1,2,3,4) and HESA (0,1,2,3,4) will be provided by treatment group and by visit, respectively.
- The percent of subjects with improvement vs no change from baseline in the C-P category, MELD category based on category of 40+, 30 to 39, 20 to 29, 10 to 19, < 9, Conn and HESA will be analyzed by the Cochran–Mantel–Haenszel test stratified by baseline category, respectively.

The graphics for the 4 scores by treatment and by visit will be presented.

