### 5.1. Inclusion Criteria

To be eligible to participate in the study, at the Screening Visit each subject must:

1. Be adequately informed and understand the nature and risks of the study and must be able to provide a signature and date on the informed consent form (ICF).
2. Be at least 18 and no more than 80 years of age at the Screening Visit. Subjects may be male or female.
3. Have known or evident liver cirrhosis. Diagnosis of liver cirrhosis may be based on clinical, radiological, and or histological criteria, including 1 or more of the following:
  - a. Liver biopsy (documented by histology);
  - b. Clinical evidence of cirrhosis, defined as aspartate aminotransferase greater than alanine aminotransferase, platelet count less than 150,000  $\mu\text{L}$ , and nodular liver surface on computed tomography scan or magnetic resonance imaging;
  - c. Clinical evidence of significant portal hypertension, based on current or history of gastroesophageal varices on endoscopy, evidence of portosystemic collaterals (on contrast computed tomography or magnetic resonance imaging with contrast), and/or presence of ascites;
  - d. Transient elastography consistent with cirrhosis, ie, a result of greater than 13.0 kPa.
4. A history of at least 1 or more documented episodes of HE within the last 12 months.
5. Hyperammonemia (defined as an ammonia level  $\geq 37 \mu\text{mol/L}$ ) at screening.
6. Currently using lactulose (minimum of 5 days prior to Day -1).
7. If using rifaximin at the Screening Visit, it must be discontinued at least 5 days before the first dose of study drug.
8. If female, be of non-childbearing potential (history of hysterectomy, bilateral oophorectomy, bilateral tubal ligation; or postmenopausal with no history of menstrual flow in the 12 months prior to the Screening Visit); or, if of childbearing potential, be non-pregnant, non-lactating and agree to use 2 forms of effective contraception when with a male partner for the duration of the study and for 28 days after any active treatment period. Acceptable forms of contraception include hormonal measures (oral contraceptive pills, contraceptive patch, contraceptive ring, injections), intrauterine devices, double barrier method (condom plus diaphragm, condom or diaphragm plus spermicidal gel or foam, surgical sterilization of the male partner), and abstinence.

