## 5.2. Exclusion Criteria

A subject is ineligible for study participation if, at the Screening Visit, the subject:

1. Is from a vulnerable population, as defined by the US Code of Federal Regulations (CFR) Title 45, Part 46, Section 46.111(b) and other local and national regulations, including but not limited to, employees (temporary, part-time, full time, etc.) or a family member of the research staff conducting the study, or of the sponsor, or of the contract research organization, or of the Institutional Review Board (IRB)/Independent Ethics Committee (IEC).
  2. Has a history of sensitivity or allergy to MNK6106, ORN, PAA, L-ornithine L-aspartate, phenylbutyrate or rifaximin.
  3. Has expectation of liver transplantation within 1 month after the Screening Visit.
  4. Had placement of a portosystemic shunt or transjugular intrahepatic portosystemic shunt within 3 months before the Screening Visit.
  5. Has a Model for End Stage Liver Disease (MELD) score greater than 25.
  6. Has HESA score Grade 4.
  7. Had gastrointestinal bleeding within 3 months of the Screening Visit.
  8. Has severe renal impairment (Creatinine Clearance rate no more than 30 mL/min) calculated using the Cockcroft-Gault formula.
  9. Has intercurrent infection or active spontaneous bacterial peritonitis.
  10. Has known immune compromised status (not related to disease/condition under study), including but not limited to individuals who have undergone organ transplantation or who are known to be positive for the human immunodeficiency virus (HIV).
  11. Has any solid tumor malignancy currently diagnosed or undergoing therapy or has received therapy for any solid tumor malignancy in the 5 years prior to the Screening Visit; with the exception of treated and cured basal cell carcinoma, treated and cured squamous cell carcinoma of the skin, and treated and cured carcinoma in situ of the cervix.
  12. Has a history of prior cognitive impairment.
  13. Has a history of psychotic disorders including but not limited to schizophrenia, dementia, or other severe psychotic disorders that would interfere with evaluation of HE.
  14. Has a positive screening result for drugs and alcohol (except for subjects positive to cannabinoids).
-

- 
15. Has a QT interval corrected using Fridericia's Formula (QTcF) of at least 500 msec at screening.
  16. Has any of the following laboratory abnormalities at the Screening Visit:
    - Hemoglobin < 8.0 g/dL.
    - Platelet count < 25,000 cells/ $\mu$ L.

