### **10.6. Clinical Function Scoring**

#### **10.6.1. Conn Score**

Subjects will be assessed at screening and every day using the Conn score, to determine if they have a worsening in HE, indicated as an increase in their score by 1 or more grades. The Conn score (also known as the West Haven Criteria) is an extensively used grading scale for assessment of HE severity. It consists of a 5-point scale (Grade 0 to 4) as follows:

- Grade 0: no apparent personality or behavioral abnormality;
- Grade 1: trivial lack of awareness, euphoria or anxiety; shortened attention span; impairment of addition or subtraction;
- Grade 2: lethargy; disorientation for time; obvious personality change; inappropriate behavior;
- Grade 3: somnolence to semi-stupor, responsive to stimuli; confused; gross disorientation; bizarre behavior;
- Grade 4: coma; unable to test mental state.

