#### **10.6.2. HESA Score**

The HESA score will be assessed at the screening visit to assess study eligibility, and will also be assessed on Days 1 through 5/ET, to determine if subjects have a worsening in their condition. The HESA implements objective ways of measuring the parameters of the West Haven scale. The HESA utilizes clinical indicators combined with validated neuropsychological tools and well-defined criteria for each stage (see HESA algorithm in Section 10.8). The use of the HESA is still limited and its metric characteristics have not been fully analyzed. One favorable characteristic of the HESA is that it identifies low grades of HE precisely. It consists of a 5-point scale (Grade 0 to 4), with 4 indicating most severe ([Hassanein et al, 2008](#)).

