### 10.6.3. MELD Score

Subjects will be assessed at the screening visit to assess eligibility into the trial. Additionally, subjects will be assessed at each visit using the MELD score, to determine if they have a worsening in their condition. MELD is a scoring system for assessing the severity of chronic liver disease. It was initially developed to predict mortality within 3 months of surgery in patients who had undergone a transjugular intrahepatic portosystemic shunt procedure and was subsequently found to be useful in determining prognosis and prioritizing for receipt of a liver transplant. MELD uses the patient's values for serum bilirubin, serum creatinine, and the INR for prothrombin time to predict survival. It is calculated using the following formula:

$$\text{MELD} = 3.78 \times \ln[\text{serum bilirubin (mg/dL)}] + 11.2 \times \ln[\text{INR}] + 9.57 \times \ln[\text{serum creatinine (mg/dL)}] + 6.43$$

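### Section 9.5 compares improvement with no change and leaves worsened subjects unassigned; MELD 9 has no class, and percent change is undefined at Conn or HESA grade 0

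*Combined protocol and SAP*

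**What the plan says.** Section 9.5 (Other Analyses) sets out three analyses of the Child-Pugh (C-P), MELD, Conn and HESA scores.

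- Change scores: "The change and percent change of C-P, MELD, Conn, and HESA scores by visit will be summarized", then analysed by ANCOVA with multiple imputation.
- Category percentages by arm and visit, with classes given as "MELD (40+, 30-39, 20-29, 10-19, <9". The same MELD cut points are repeated for the CMH test.
- A CMH test stratified by baseline category, whose outcome is "The percent of subjects with improvement vs no change from baseline in the C-P category", and the same for MELD class, Conn and HESA.

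Section 10.6 says why three of these scores are recorded. Conn is scored "to determine if they have a worsening in HE, indicated as an increase in their score by 1 or more grades". HESA is scored "to determine if subjects have a worsening in their condition". For MELD, "subjects will be assessed at each visit using the MELD score, to determine if they have a worsening in their condition".

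On entry, Section 5.1 asks for "A history of at least 1 or more documented episodes of HE within the last 12 months". The only Conn or HESA limit in Section 5.2 is "Has HESA score Grade 4", and its MELD limit is an upper one (above 25 excluded). Section 9.3.3 only points back to Section 9.5, and Section 10.6 gives no MELD classes.

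**The concern.** **Worsening has no place in the CMH outcome.** Two levels are named, and a worsened subject is in neither. Excluding such subjects defines the denominator by a post-randomisation outcome, so an arm can look better because more of its subjects deteriorated. Counting them as unchanged removes that bias but makes the test blind to deterioration. On either reading, a stratum in which nobody can improve (Conn 0, HESA 0, C-P class A, lowest MELD class) contributes nothing. A move from Conn 0 to 1, which Section 10.6.1 defines as worsening, therefore never enters the test. The study is open-label, and leaving the choice of rule until the data are in is an avoidable freedom.

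**MELD 9 is unclassified.** The classes go from 10–19 to below 9, so an eligible subject may have no table row and no CMH stratum.

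**Percent change can be a division by zero.** Conn and HESA both start at 0, and a past episode of encephalopathy is enough for entry. The percent-change summary would then silently cover only subjects at baseline grade 1 or higher.

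**Working it through.** The plan gives no figure to reproduce here. Arm size is 48/4 = 12 (Section 9.1). All improvement and worsening counts below are assumptions.

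**1a. CMH, one stratum.** Arms X and Y have 12 subjects and 4 improved each. Nobody worsens in Y; 0, 2, 4 or 6 worsen in X. With *a* improved among n_X, *m* improved overall and *N* subjects: E = n_X·m/N, V = n_X·n_Y·m(N−m)/[N²(N−1)], chi-square = (a−E)²/V.

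| Worsened in X | X, worsened dropped | Y | Chi-square | p |
|---|---|---|---|---|
| 0 | 4/12 = 33% | 4/12 = 33% | 0 | 1.00 |
| 2 | 4/10 = 40% | 33% | 0.10 | 0.75 |
| 4 | 4/8 = 50% | 33% | 0.53 | 0.47 |
| 6 | 4/6 = 67% | 33% | 1.70 | 0.19 |

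Last row: E = 6×8/18 = 2.667; V = 6×12×8×10/(324×17) = 1.046; (4−2.667)²/1.046 = 1.70. With everyone kept and worsened counted as not improved, every row is 4/12 against 4/12 and chi-square is 0.

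**1b. CMH, stratified as planned.** Per arm, take 6 subjects at grade 0 and 6 at grade 1 or higher (treated as one stratum for simplicity), with 2 improved per arm in the upper stratum. In X, 1+1, 2+2 or 3+3 worsen across the two strata; in Y, none.

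- Worsened dropped: the upper stratum gives 40%, 50% or 67% in X against 33% in Y. At 3+3 this is 2/3 against 2/6, chi-square 0.80, p = 0.37. The grade-0 stratum has a−E = 0 and V = 0.
- Worsened pooled with unchanged: 2/6 against 2/6, chi-square 0, p = 1.00 in every case.
- Ordered scores −1/0/+1 with the CMH mean-score test, V = (n_X·n_Y/N)·SS/(N−1) per stratum. At 3+3:
  - Grade 0: X sums to −3, expected −1.5, difference −1.5; SS = 3 − 9/12 = 2.25; V = 3×2.25/11 = 0.614.
  - Upper: X sums to −1, Y to 2, expected 0.5, difference −1.5; SS = 7 − 1/12 = 6.917; V = 3×6.917/11 = 1.886.
  - Chi-square = (−3)²/(0.614+1.886) = 3.60, p = 0.058, against X.
  - The 1+1 and 2+2 cases give 0.71 (p = 0.40) and 2.00 (p = 0.16), also against X.

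**2. MELD.** Nine is the only integer in no class. By the Section 10.6.3 formula with bilirubin 1.5 mg/dL, INR 1.1 and creatinine 1.0 mg/dL: 3.78·ln(1.5) + 11.2·ln(1.1) + 9.57·ln(1.0) + 6.43 = 1.53 + 1.07 + 0 + 6.43 = 9.03. At that INR and creatinine, any bilirubin from 1.31 to 1.69 mg/dL rounds to 9. No rounding rule is given, so unrounded scores between bins are also unclassed: bilirubin 4, INR 1.7 and creatinine 1.2 give 5.24 + 5.94 + 1.74 + 6.43 = 19.36 (terms kept unrounded in the sum).

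**3. Percent change.** 100 × (post − baseline)/baseline has a zero denominator at grade 0. Conn runs 0–4 (Section 10.6.1), as does HESA (Section 10.6.2), and the grading sheet in Section 10.8 assigns grade 0 by default. Nothing in Sections 5.1 or 5.2 requires grade 1 or higher. C-P starts at 5 points and does not have this problem.

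**The case against.** The strongest reply is about weight. These scores support no listed endpoint; Amendment 2 removed them from the secondary endpoints. They sit under other analyses in a study that Section 9.3 calls exploratory, with no hypothesis to test. Worsening is still visible in the absolute-change ANCOVA, the category percentages and the graphics. Many CNS events are also captured as adverse events of special interest (Section 10.3.5). All of that stands and limits the harm to this one test and these tables.

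It can also be said that a percent of subjects normally means all assessed subjects, so that no change is shorthand for not improved. That reading is possible, but the text does not state it, and under it the test says nothing about worsening. Even in the extreme assumed case the biased reading reaches only p = 0.19, so a nominally significant false signal is not shown. The direction is still wrong.

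The ordered test has its own weakness: 4 improved and 4 worsened average to zero, the same as no change. That is true, and it is why the three counts must be shown beside it. The MELD slip is editorial and has no direction.

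Finally, Section 9.5.2 refers to a statistical analysis plan for exposure periods. The text available contains no separate plan, so rules placed there could not be checked; Section 9.5 itself defers nothing on these points.

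**Conclusion.** All three points hold on the wording of Section 9.5, and nothing elsewhere in the text cures them. The CMH outcome omits a category that Section 10.6 says three of the scores are there to detect, and the unstated rule determines the direction of the result. In the assumed example with six worsened subjects in one arm, the test leans towards that arm if they are dropped, shows nothing if they are pooled, and leans against it if worsening is an ordered level. The sizes rest entirely on assumed counts. That the rule is missing, that a MELD of 9 has no class and that percent change fails at grade 0 do not depend on those counts. How many subjects would be affected cannot be told from the documents. This is a should-fix in supportive analyses and leaves the primary ammonia analysis untouched.

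**What to change.** Reword Section 9.5 as follows.

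- Class every subject who has both a baseline score and a score at the analysed visit as worsened, unchanged or improved. Name the visit or visits, since the CMH bullet names none. Show n (%) of all three by arm on that one denominator, and state how many scores are missing.
- Compare arms with the CMH mean-score test on −1/0/+1, stratified by baseline category. This also counts worsening from grade 0.
- If a two-level test is preferred, define it as improved against not improved (unchanged or worsened) in the same subjects, with the number worsened by arm beside it.
- Round MELD to an integer and make the lowest class 9 or below, in both places where the classes appear.
- Drop percent change for Conn and HESA and keep absolute change.

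The cost is wording in one section. No new data, visits or subjects are needed.
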